#### ***8.4.5 Vital Signs and Physical Examination***

Actual value and change from baseline for vital sign and pulse oximetry results including blood pressure (SBP[mmHg], DBP[mmHg]), heart rate (bpm), respiratory rate (bpm), temperature (C), SpO2(%) and flow rate (L/min) will be summarized at each scheduled visit.

Physical examination results including height, weight, and BMI will be summarized by the absolute value and change from baseline at each scheduled visit during the study. Height will presented for Screening only. Baseline is the Screening visit.

Baseline for vital signs is defined as the average of Screening and Day 1 measurements taken before the first dose of GBT440.

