Study Evaluations	
Safety Assessments
 
Subject safety and tolerability will be monitored throughout the study using standard measures, including physical examinations, vital signs (including blood pressure, pulse rate, body temperature, respiratory rate), 12-lead ECGs, safety labs (hematology, serum chemistry, urinalysis, coagulation, and pregnancy tests), concomitant medication usage and adverse event (AE) monitoring.
 
Clinical Assessments
 
Oxygen Titration Test (OTT)
 
The OTT will be used to assess the subjects' O₂ requirements at rest and with exercise, as measured by pulse oximetry and arterial blood gases (ABG). Subjects will exercise by walking along a 6MWT or equivalent course.
 
Refer to the separate OTT manual for complete instructions on the conduct of the OTT. The flow of O₂ will be titrated to maintain a stable SpO₂ of 89 to 92%.
 
Oxygen Saturation Measurement
 
The measurement of peripheral oxygen saturation (SpO₂) will be performed using the pulse oximeter provided by the Sponsor.
 
Screening and Day 1 Visit
 
SpO₂ measured at these visits are to determine eligibility for inclusion into the study, and will be performed at rest, breathing room air.

Prior to measuring SpO₂ breathing room air, subjects must be rested for at least 10 minutes breathing their usually prescribed flow rate of O₂. Then the subject's supplemental O₂ should be turned off to measure resting, room air SpO₂ as noted below.

- Resting oxygen saturation (SpO₂) between 85 and 88% for at least 30 consecutive seconds while breathing room air (refer to [Section 4.1](#) Inclusion Criteria)

Or

- Resting SpO₂ <85% for 10 consecutive seconds or, if in the opinion of the site staff, it is not safe or tolerable for the subject to continue without using their supplemental oxygen for 10 consecutive seconds whilst the SpO₂ is <85%.

Either of these 2 criteria should be met at both screening and Day 1 visits.

Arterial Blood Gases (ABG)

Arterial blood samples will be taken at each scheduled OTT: Day 1 (baseline), Days 30, 90, and 120. Two samples will be drawn at each test:

- Prior to the beginning of the test (i.e., prior to beginning to walk) while resting and breathing room air (i.e., with no oxygen being delivered to the subject) and
- Immediately after completion of the OTT while receiving oxygen at the flow rate being delivered at the end of the test

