5.3.2 Medical History and Demographic Data

Medical history includes currently active and past clinically significant diseases, surgeries, cancer history (including prior cancer therapies and procedures), smoking history, use of alcohol and drugs of abuse within the previous year, and IPF-associated conditions including but not limited to pulmonary hypertension, gastroesophageal reflux disease, and sleep disordered breathing.

Medical conditions that are a result of side effects (e.g., rash or diarrhea) from concomitant medications (e.g., pirfenidone or nintedanib) should be clearly defined and entered into the eCRF.

Any medical condition present at baseline should be followed during the study, and a change from the baseline status (intensity or frequency) should be reported as an AE by the Investigator (refer to [Section 10.1](#)).

All concomitant medications (e.g., prescription drugs, over-the-counter drugs, herbal/homeopathic remedies, nutritional supplements) used by the subject within 14 days prior to the screening visit should be entered on the Concomitant Medications eCRF. A start date should be entered for all medication items entered into the Concomitant Medications eCRF, including those medications used chronically.

Demographic data will include age (date of birth), sex, and self-reported race/ethnicity.

5.3.3 *Physical Examination*

A complete physical examination should include the following: an evaluation of the head, eyes, ears, nose, throat, and the cardiovascular, dermatological, musculoskeletal, respiratory, gastrointestinal, and neurological systems. A rectal or pelvic examination is not required. Any abnormality identified during screening should be recorded on the eCRF.

At subsequent visits, limited, symptom-directed physical examinations should be performed. Changes from baseline abnormalities should be recorded in the subject's study source documents. New or worsened abnormalities should be recorded as AEs on the Adverse Event eCRF.

Vital signs will include measurements of respiratory rate, heart rate, body temperature, systolic and diastolic blood pressure and oxygen saturation (SpO₂) by pulse oximetry. Blood pressure and SpO₂ measurements should be taken while the subject is in a seated or semi-recumbent position, and resting for at least 5 minutes.

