5.5.2 Oxygen Saturation Measurement

The measurement of peripheral oxygen saturation (SpO₂) will be performed using the pulse oximeter provided by the Sponsor.

Screening and Day 1 Visit

SpO₂ measured at these visits are to determine eligibility for inclusion into the study, and will be performed at rest, breathing room air.

Prior to measuring SpO₂ breathing room air, subjects must be rested for at least 10 minutes breathing their usually prescribed flow rate of O₂. Then the subject's supplemental O₂ should be turned off to measure resting, room air SpO₂ as noted in [Section 4.1 Inclusion Criteria](#) and reproduced below.

- Resting oxygen saturation (SpO₂) between 85 and 88% for at least 30 consecutive seconds while breathing room air (refer to [Section 4.1 Inclusion Criteria](#))

Or

- Resting SpO₂ <85% for 10 consecutive seconds or, if in the opinion of the site staff, it is not safe or tolerable for the subject to continue without using their supplemental oxygen for 10 consecutive seconds whilst the SpO₂ is <85%.

Either of these 2 criteria should be met at both screening and Day 1 visits.

Vital Sign Assessments

At all scheduled vital sign assessments, SpO₂ will be measured with the subject breathing supplemental O₂, set at their usual O₂ flow rate, and after resting for at least 5 minutes. SpO₂ will be also be collected during conduct of the OTT and 6MWT (refer to the respective manuals for complete instructions).

Before recording the SpO₂ value in the eCRF, the study staff should ensure the measurement is stable, which may require continuous or repeated measurements and ensuring the subject is adequately rested.

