- a. All screening evaluations must be completed and reviewed prior to Day 1 (Visit 2) to confirm the subject meets all eligibility criteria prior to dosing.
- b. All subjects who discontinue study or study drug prior to study completion and who are unwilling or unable to complete the remaining scheduled visits should return to the study site to complete all ET assessments (see [Section 6](#))
- c. Written informed consent must be obtained and documented prior to performing any study-specific screening procedure
- d. Demographics, medical history and baseline conditions obtained at screening should be reviewed again and any changes since screening noted in the eCRF
- e. After informed consent but prior to randomization only SAEs resulting from a protocol-mandated intervention should be reported. After randomization, all adverse events will be reported until study completion (Day 120).

- f. Includes evaluation of the head, eyes, ears, nose and throat and cardiovascular, respiratory, musculoskeletal, gastrointestinal, neurological, dermatologic systems. No rectal or pelvic examination is required. Record any observed abnormalities in the eCRF. At subsequent visits record new or worsened clinically significant findings on the eCRF.
- g. Perform a limited, symptom-directed examination as clinically indicated. Record new or worsened clinically significant findings in the eCRF.
- h. Includes heart rate, respiratory rate, systolic and diastolic blood pressure and temperature measured in a semi-recumbent or supine position and resting for at least 5 minutes.
- i. Performed at the time of Vital Signs assessment, with the subject breathing their supplemental O2 delivered at the usual prescribed rate and after the subject has rested for at least 5 minutes.
- j. Perform 12-lead ECG after the subject has been resting in a semi-recumbent or supine position for at least 5 minutes.
- k. Perform for all female subjects who are not post-menopausal or surgically sterile. On Day 1, urine pregnancy must be performed before any other assessments. The Investigator is to ensure that the result is negative prior to completing any other study related assessments and prior to administering investigational product to the subject.
- l. If a urine pregnancy test on Day 1 is positive, confirm the result with a serum pregnancy test. The serum pregnancy test must be available (and negative) prior to Day 1 dosing.

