- e After informed consent but prior to randomization only serious adverse events (SAEs) resulting from a protocol-mandated intervention should be reported. After randomization, all AEs will be reported until study completion (Day 120).
- f Includes evaluation of the head, eyes, ears, nose and throat and cardiovascular, respiratory, musculoskeletal, gastrointestinal, neurological, dermatologic systems. No rectal or pelvic examination is required. Record any observed abnormalities in the eCRF. At subsequent visits, record new or worsened clinically significant findings on the eCRF.
- g Perform a limited, symptom-directed examination as clinically indicated. Record new or worsened clinically significant findings in the eCRF.
- h Includes heart rate, respiratory rate, systolic and diastolic blood pressure and temperature measured in a semi-recumbent or supine position and resting for at least 5 minutes.
- i Performed at the time of Vital Signs assessment, with the subject breathing their supplemental O₂ delivered at the usual prescribed rate and after the subject has rested for at least 5 minutes. On Screening and Day 1 visits must be performed prior to other assessments to ensure eligibility.
- j Perform 12-lead ECG after the subject has been resting in a semi-recumbent or supine position for at least 5 minutes.
- k Perform for all female subjects who are not post-menopausal or surgically sterile. On Day 1, urine pregnancy must be performed before any other assessments. The Investigator is to ensure that the result is negative prior to completing any other study related assessments and prior to administering investigational product to the subject.
- l If a urine pregnancy test on Day 1 is positive, confirm the result with a serum pregnancy test. The serum pregnancy test must be available (and negative) prior to Day 1 dosing.
- m Instructions for per protocol performance of the oxygen titration, 6-minute walk (and Borg Dyspnea Scale) and ABG tests are provided in the procedure manual.
- n The ATAQ, SGRQ and End of Treatment questionnaires should be self-administered by the subject using the paper forms provided by the Sponsor prior to all other non-PRO assessments and before the subject receives any disease-status information during that assessment. The End of Treatment questionnaire is to be administered at the Day 120 visit, if it was not administered at the Day 90 visit.

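### Could room-air eligibility readings slip into the baseline SpO2 and O2 flow of the SAP 8.4.5 vital-signs table?

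*SAP*

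**What the plan says.** SAP 8.4.5 introduces the table as "Actual value and change from baseline for vital sign and pulse oximetry results including blood pressure", continues through heart rate, respiratory rate and temperature to SpO2 and flow rate, and summarizes them at each scheduled visit. It then states that "Baseline for vital signs is defined as the average of Screening and Day 1 measurements taken before the first dose of GBT440". SAP 7.2 gives the general default: the last value before first dose, or the average where several pre-dose assessments are collected, with vital signs as its example. Neither section names a breathing condition.

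Protocol 5.5.2 describes two resting readings. Of Screening and Day 1 it says "SpO₂ measured at these visits are to determine eligibility for inclusion into the study, and will be performed at rest, breathing room air". Of vital signs it says "At all scheduled vital sign assessments, SpO₂ will be measured with the subject breathing supplemental O₂, set at their usual O₂ flow rate".

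The protocol's lists of vital signs differ. Section 5.3.3 says "Vital signs will include measurements of respiratory rate, heart rate, body temperature, systolic and diastolic blood pressure and oxygen saturation (SpO₂) by pulse oximetry". The synopsis has "vital signs (including blood pressure, pulse rate, body temperature, respiratory rate", and footnote h of Tables 15-1 and 15-2 has "Includes heart rate, respiratory rate, systolic and diastolic blood pressure and temperature measured in a semi-recumbent or supine position"; neither names SpO2. In both schedules SpO2 has its own row, and footnote i places it at the vital-signs assessment on usual oxygen. Table 15-2 footnote i then adds "On Screening and Day 1 visits must be performed prior to other assessments to ensure eligibility".

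**The concern.** Each subject has two kinds of resting SpO2 at exactly the two visits that SAP 8.4.5 averages. The sentence introducing the table names pulse oximetry beside vital signs, while the baseline sentence names vital signs only. If pulse oximetry is not a vital sign, SAP 7.2 applies, and it averages pre-dose assessments without regard to breathing condition. Table 15-2 footnote i blurs the two readings further by linking an on-oxygen row to eligibility, which is a room-air test.

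If room-air readings entered the baseline, it would be low because subjects are selected for low room-air saturation, while later vital-sign values are on oxygen. SpO2 would then seem to improve with no drug effect, and there is no control arm to expose it. Flow rate could be affected too, if room-air readings were stored with a flow of zero.

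**Working it through.** The documents state no figure on this point, so the check is mainly a comparison of texts.

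**1. Which reading fits SAP 8.4.5?**

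| Feature of the SAP 8.4.5 table | On-oxygen vital-sign reading | Room-air eligibility reading |
|---|---|---|
| Section on vital signs | Yes: Protocol 5.3.3, 5.5.2, footnote i of both schedules | No: a separate eligibility check in Protocol 5.1 and 5.5.2 |
| Summarized at each scheduled visit | Yes: the SpO2 row is marked at every visit | No: Screening and Day 1 only |
| Listed beside a flow rate in L/min | Yes: taken at the usual flow | No: oxygen is turned off |

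Only the on-oxygen reading fits all three.

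**2. Do the shorter lists exclude SpO2?** Both are worded as inclusive lists and need not be complete. The schedules give SpO2 its own row, but footnote i ties that row to the vital-signs assessment.

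**3. Does the SAP 7.2 default lead elsewhere?** It averages repeated assessments of a given variable. For vital-sign SpO2 that is again the Screening and Day 1 average. Pooling would mean treating a room-air eligibility check as the same variable as saturation on usual oxygen, and no text says so. The same holds for SpO2 recorded during the oxygen titration and 6-minute walk tests, which have their own procedures and manuals.

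**4. What would pooling do?** Let w be the share of room-air readings in the baseline. With no true change,

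shift = w × (on-oxygen SpO2 − room-air SpO2).

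- On-oxygen readings only, w = 0: shift = 0.
- Two room-air and two on-oxygen readings, w = 2/4 = 0.5. Take room air at 85–88% (the first eligibility band, Protocol 4.1) and on-oxygen at 89–92% (the titration target, Protocol 5.5.1):
  - smallest: 0.5 × (89 − 88) = 0.5 points
  - mid-range: 0.5 × (90.5 − 86.5) = 2.0 points
  - largest: 0.5 × (92 − 85) = 3.5 points
- On-oxygen SpO2 of 95%: 0.5 × (95 − 88) = 3.5 to 0.5 × (95 − 85) = 5.0 points.
- Flow, if room-air readings were stored as zero: a usual flow of 4 L/min would average (4 + 4 + 0 + 0)/4 = 2 L/min.

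These figures are not bounds. The 2-of-4 weight is assumed. The titration target is not the saturation at a subject's usual flow, which the documents do not give. The second eligibility route admits subjects below 85%. The direction also depends on the sign convention: SAP 8.1, as worded, subtracts the post-baseline value from baseline, so a baseline that is too low would make the printed change more negative, although its percentage formula runs the other way.

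**5. Does Table 15-2 footnote i alter a result?** Its added sentence conflicts in wording with the room-air criterion, and with the note to the same table, which puts vital signs after the questionnaires, ECG and adverse-event review. But Protocol 4.1, 5.1 and 5.5.2 state the room-air condition outright, and footnote a of that table points to the inclusion criterion. The slip concerns the conduct of the visit and does not redefine the SAP baseline.

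**The case for a change.** The best case for a change is that the SAP covers safety only, for an abbreviated report, so the SAP 8.4.5 table is the only change-from-baseline summary of oxygen saturation it specifies. The SAP still carries a primary objective about saturation on room air, so a reader of SAP 8.4.5 alone could not tell which condition the table reports. Each schedule has a single SpO2 row and none for the room-air check, and one sentence before database lock would remove any doubt at almost no cost.

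It stands that the SAP text alone does not name the condition, and that footnote i of Table 15-2 is badly worded. It does not follow that the table would be wrong. The SAP says it was prepared in accordance with the protocol, and the protocol settles the condition for vital-sign SpO2 at all scheduled vital-sign assessments. Harm would also require the eligibility readings to share a data field with the vital-sign readings. The documents do not show how eligibility readings are stored, and the instruction on recording SpO2 in the eCRF sits under the vital-sign heading of Protocol 5.5.2. An added sentence would restate what the protocol already says and would change no number.

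**Conclusion.** No change is needed. This is missing detail that an analyst fills correctly from the protocol, alongside a clerical slip in one schedule footnote. With on-oxygen vital-sign readings the artefact is 0. The 0.5 to 3.5 points in the working should not be read as an expected bias, because they depend on pooling that no passage calls for and on saturation values the documents do not supply.

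The conclusion assumes that the analyst reads SAP 8.4.5 together with Protocol 5.3.3 and 5.5.2, and that room-air eligibility values are not merged into the vital-sign SpO2 variable. The consequence is small in any case: the sample size is not power-based, the table is descriptive, and no test or stated decision uses it. The footnote i wording can be reconciled with Protocol 4.1 and 5.5.2 if the protocol is opened for another reason; no result waits on it.

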#### ***8.4.6 12-Lead Electrocardiogram***

HR (beats/min), PR interval (ms), QRS interval (ms), QT interval (ms), and QTc F interval (ms) will be summarized by the absolute value and change from baseline (Screening) at D90.

Additionally, the number and percentage of subjects with QTcF > 450 ms, >480 ms, and >500 ms at baseline and post-baseline measurement (Day 90 and Early Termination) will

be summarized by dose level and All GBT 440. The number and percentage of subjects with increase from baseline in QTcF of > 30ms and > 60 ms will also be summarized.

## 8.5 Pharmacokinetic Analyses

Planned PK will be described in a separate analysis plan. The results will be described in the CSR.

Safety population.

# 9 STATISTICAL/ANALYTICAL ISSUES

## 9.1 Handling of Dropouts or Missing Data

Missing data will not be estimated or carried forward for any of the other summaries.

If only a partial date is available and is required for a calculation of whether a medication is concomitant or an AE is treatment-emergent, the following standards will be applied:

- Start dates (e.g., AE onset date or start date of medication)  
For missing start day only - Day will be imputed as the first day of the month (i.e., 1) with the following exception: if the partial date falls in the same month and year as the date being used in the calculation (e.g., first dose date, informed consent date), then the partial date will be imputed to equal the date being used for the calculation.

For missing start day and month - Day and month will be imputed as the first day of the year (i.e., 1 January) with the following exception: if the partial date falls in the same year as the date being used in the calculation (e.g., first dose date, informed consent date), then the partial date will be imputed to equal the date being used for the calculation.

- Stop dates (e.g., AE resolution date or stop date of medication)  
For missing stop day only - Day will be imputed as the last day of the month (i.e., 28, 29, 30, or 31)

For missing stop day and month - Day and month will be imputed as the last day of the year (i.e., 31 December)

Any partial dates will be displayed in data listings without imputation of missing days and/or months (e.g., MAR2011, 2009). No other imputation of missing data will be performed.

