### ***8.3.3 Prior and Concomitant Medications***

All prior and concomitant medications will be coded using WHO Drug Dictionary Enhanced March 2017. Concomitant medications are defined as medications with start date or end date on or after the date of first dose and start date before the date of the last dose + 30 days or are ongoing at the time of first dose. Prior medications are defined as medications with a stop date before the date of first dose of study drug.

Prior and concomitant medications will be listed only.

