#### **8.4.3 Adverse Events**

Each reported AE term will be mapped to PT and SOC using the MedDRA Version 20.

Treatment-emergent adverse events (TEAEs) are defined as any event that occurs or worsens on or after the first dose of study drug and within 30 days after the last dose. Treatment-emergent adverse events (TEAEs) will be summarized based on the number (%) of subjects experiencing events by SOC and PT. The denominator for the percentage will be based on the number of subjects in the Safety population (i.e., those that received at least one dose of study drug).

A subject reporting the same AE more than once will be counted only once when calculating incidence 1) within a given system organ class, and 2) within a given system organ class and preferred term combination. For such cases, the maximum CTCAE toxicity grade and strongest causal relationship to study treatment for the event will be used in the incidence calculations.

An overall summary will be presented that includes the number of TEAEs and the number and percentage of subjects who experienced at least one TEAE. This summary will also include TEAEs  $\geq$  Grade 3, TEAEs possibly/probably related to study drug, serious adverse events (SAEs), TEAEs leading to discontinuation of study drug, and deaths.

Summaries of the following TEAEs will be provided by SOC and PT:

- All TEAEs
- Treatment-related AEs
- TEAEs by maximum severity, table includes a summary of AEs grade 3 or higher
- Serious TEAEs (AE listing)
- TEAEs that led to dose modification or permanent discontinuation of GBT 440 (listing only )

Summaries presented by SOC and PT will be ordered alphabetically for SOC and descending frequency within SOC of PT based on the total GBT 440 group.

All AE data will be summarized for each dose level (900 mg, 1500mg).

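### SAP 9.1 can set a partial start date to the first-dose date when the recorded stop date is already earlier, so a record that ended before dosing becomes treatment-emergent or concomitant

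*SAP*

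**What the plan says.** SAP 9.1 (Handling of Dropouts or Missing Data) applies its date rules when a partial date is "required for a calculation of whether a medication is concomitant or an AE is treatment-emergent".

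- **Start day missing:** use the first of the month, except that "if the partial date falls in the same month and year as the date being used in the calculation" the start becomes that reference date. First dose is one of the SAP's examples of a reference date.
- **Start day and month missing:** use 1 January, except that "if the partial date falls in the same year as the date being used in the calculation" the same substitution is made.
- **In both exceptions:** "then the partial date will be imputed to equal the date being used for the calculation".
- **Closing sentence:** "No other imputation of missing data will be performed".

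Three definitions use the result.

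- **Treatment-emergent adverse event (TEAE), SAP 8.4.3:** "any event that occurs or worsens on or after the first dose of study drug and within 30 days after the last dose".
- **Concomitant, SAP 8.3.3:** "Concomitant medications are defined as medications with start date or end date on or after the date of first dose", together with a start before last dose plus 30 days. A medication ongoing at first dose also qualifies.
- **Prior, SAP 8.3.3:** "Prior medications are defined as medications with a stop date before the date of first dose of study drug".

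**The concern.** Moving an uncertain onset to first dose is a sensible cautious choice when the stop date is missing or falls on treatment. It is not cautious when the sponsor holds a stop date before first dose, because the imputed start then contradicts the recorded data. Neither start-date bullet makes an exception for that case, and nothing elsewhere in the SAP caps the imputed start at a known stop.

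The SAP covers safety only, for an abbreviated report. Its safety endpoint (SAP 3.1) is the frequency and severity of TEAEs and tolerability. A false TEAE would enter the incidence tables. For medications, one record would satisfy two categories that read as alternatives.

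**Working it through.** The plan gives no figure to reproduce. The check applies the written rules to test records.

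**Inputs**
- Start-date rule: SAP 9.1.
- TEAE definition: SAP 8.4.3. It uses onset or worsening, not resolution.
- Concomitant and prior definitions: SAP 8.3.3.
- Screening window, Day -21 to Day -1: Protocol 5.3.1 and Appendix A.
- Dose group size, up to about 16: SAP 4.
- First dose on 20 Jun 2017: assumed, for illustration.

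**Test records under the rule as written**

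| Recorded start | Recorded stop | Imputed start | TEAE (if an AE) | Concomitant (if a drug) | Prior (if a drug) |
|---|---|---|---|---|---|
| (a) Jun 2017 | 12 Jun 2017 | 20 Jun 2017 | yes | yes | yes |
| (b) 2017 | 10 Mar 2017 | 20 Jun 2017 | yes | yes | yes |
| (c) May 2017 | 12 Jun 2017 | 1 May 2017 | no | no | yes |

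- In (a) the imputed start is 20 - 12 = 8 days after the stop.
- In (b) it is 21 + 30 + 31 + 20 = 102 days after the stop. This record only shows the mechanics. Without rescreening, Protocol 5.3.2 collects drugs used from at most 21 + 14 = 35 days before Day 1. Moving the stop in (b) to 12 Jun changes none of the classifications.
- Record (c) is classified correctly, so the fault is confined to starts that share the first-dose month or year.

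**The same records under the fix below**
- (a) Start becomes 1 Jun 2017, before the 12 Jun stop: not a TEAE, not concomitant, prior.
- (b) Start becomes 1 Jan 2017, before the 10 Mar stop: not a TEAE, not concomitant, prior.
- (c) Unchanged.

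**How often a screening day shares the first-dose month or year**

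Assume the first-dose day is uniform over a 30-day month. Of the 21 screening days, min(d - 1, 21) share the month when first dose falls on day d.

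- Days 1 to 22 contribute 0 + 1 + ... + 21 = 231. Days 23 to 30 contribute 8 × 21 = 168.
- Mean = (231 + 168)/30 = 13.3 days, and 13.3/21 = 63%. Enumerating the 2017 calendar gives 64%.
- For the year: (231 + 343 × 21)/(365 × 21) = 7,434/7,665 = 97%.

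Among all onset and stop pairs within Day -21 to Day -1 with the onset day missing, weighted equally over 2017 first-dose dates, the written rule makes 53% treatment-emergent. Capping the imputed start at the known stop makes it 0%. All three percentages are conditional on a partial start. The 53% also requires a known pre-dose stop.

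**Size of one error:** 1/16 = 6.25 percentage points.

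**The case against.** **The start date may not be needed.** SAP 9.1 imputes only dates that the classification requires. If a complete stop date precedes first dose, the answer is arguably settled already, and for medications the prior class depends on the stop alone. This is a fair reading, but the SAP does not state it. The TEAE and concomitant definitions both refer to the start, and neither lets an earlier stop override it. A programmer following the text could properly impute.

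**Few AEs can be affected.** This stands. Protocol 10.3 limits pre-dose reporting to serious adverse events (SAEs) from protocol-related interventions, as does footnote e of both schedules. Protocol 10.1, the widest wording, adds AEs from such interventions. These events follow dated procedures, and SAEs are reported within 24 hours. A missing onset day with a known pre-dose resolution should be uncommon, and a year-only onset is barely plausible.

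**The medication effect changes no summary.** This also stands. SAP 8.3.3 only lists medications, and SAP 9.1 displays partial dates unimputed, so the true stop stays visible.

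A reader might infer two stronger points that the documents do not support.

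- **That the exception is the usual case.** The 63% and 97% are shares of screening days, not of AEs or medications. The documents do not say how many records have partial starts, or that year-only medication starts are common.
- **That a restricted drug stopped before dosing would become a false deviation.** Protocol 8.5.2 already bars these drugs from 14 days before screening, and Protocol 5.3.2 collects drugs from the same point. Such a drug is therefore a departure whatever start is imputed. The SAP derives no deviations from the concomitant class; SAP 8.2 lists only inclusion and exclusion violations.

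**Conclusion.** The rule is wrong as written for one identifiable type of record: a partial start that shares the first-dose month (day missing) or year (day and month missing), with a recorded stop before first dose. For an AE the error reaches the TEAE tables. For a medication it is a contradictory class in a listing.

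The practical effect is probably small, and zero affected records is quite possible. The documents give no count. The 6.25 points show what one misclassified AE subject would mean in a group of 16; they do not forecast that one will occur. The conclusion rests on a literal reading of SAP 9.1, in which the limit to dates required for the calculation does not clearly exclude these records. The substitution should stay for starts whose stop is missing or on or after first dose.

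**What to change.** Add to both start-date bullets in SAP 9.1 that the exception does not apply when the recorded stop date is before first dose. The stop may be complete, or partial but clearly earlier, for example a stop month before the first-dose month. The start is then imputed as the first day of the known month or year, and never later than the stop date.

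Add one sentence, to be read with SAP 8.3.3 and 8.4.3, that a record ending before first dose is neither treatment-emergent nor concomitant.

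The cost is a sentence or two of text and one condition in the date derivation, to be made before database lock. If the recorded stop is correct, no genuine TEAE is lost, since an event that ended before dosing cannot have begun on treatment. A later change in the grade of a persistent event is recorded as a separate AE under Protocol 10.3.3.
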